6.3 Concomitant Therapy

Medications for postoperative pain management will be at the discretion of the clinical team. Our institution uses standardized postoperative medication order sets that include oxycodone, acetaminophen and/or ibuprofen.

6.4 Discontinuation of Study Intervention

Since the intervention is a treatment with device during inpatient stay, participants may choose to not continue with intervention. Women will be followed through 6 weeks postpartum regardless of their treatment assignment.

7. Study Assessments and Procedures

7.1 Study Assessments

7.1.1 Screening & Randomization

All women with a cesarean delivery will be screened for eligibility. If appropriate, study personnel will invite the patient to serve as a study participant. The initial approach will occur pre-operatively or on post-operative day 0 to ensure individual care is not modified as a result of the study design prior to randomization. Study personnel will describe the study in detail and review the study protocol with the participant. Women agreeing to participate will sign the consent form.

7.1.2 Baseline Procedures

If the patient is eligible and signs the consent form, participants be randomized to TrueRelief device or identical appearing sham device:

In addition to information collected for eligibility, the following information will be obtained from an interview with the participant and/or through the electronic medical record:

- Demographic factors (e.g., maternal date of birth, age, BMI, race/ethnicity, education, employment status, marital status, household income, insurance)
- Factors related to persistent opioid use including tobacco use, history of mental health conditions (e.g., depression, anxiety), use of anti-depressants or benzodiazepines, chronic pain conditions (e.g., back pain, migraines, fibromyalgia).

Medical history including obstetrical outcomes from the current delivery (e.g., indication for cesarean, repeat cesarean, labor prior to cesarean, operative time, type of anesthesia, perioperative complications, gestational age, birth weight, neonatal outcomes).

• Opioid and non-opioid analgesics (e.g., acetaminophen, ibuprofen) use post cesarean through discharge

7.1.3 Follow-up

Participants will be followed through 6 weeks postpartum.

7.2 Adverse Events and Serious Adverse Events

7.2.1 Definition of Adverse Events (AE)

An adverse event is any untoward medical occurrence associated with the use of a drug in humans, whether or not the event is considered drug related.

Events should be reported also if they are unexpected in nature, severity, frequency, or fit the single IRB definition of adverse event. The unexpected nature of the event is determined based on the research procedures and the characteristics of the subject population being studied. If the event is not one that is usually seen in this context or reported in the principal investigator / participant brochure, it should be considered unexpected.

7.2.2 Definition of Serious Adverse Events (SAE)

A serious adverse event is one of the following that occurs in the mother, neonate, or infant through 90 days postpartum:

- Death
- Life-threatening event
- Inpatient re-hospitalization
- Results in persistent or significant incapacity or substantial disruption of the ability to conduct normal life functions
- Other important medical event may meet the definition of serious if it jeopardizes the participant

7.2.3 Classification of an Adverse Event

7.3.3.1 Relationship to Study Intervention

All adverse events must have their relationship to study intervention assessed by the clinician who examines and evaluates the participant based on temporal relationship and his/her clinical judgment. The degree of certainty about causality will be graded using the categories below. In a clinical trial, the study product must always be suspect.

• **Definitely Related** – There is clear evidence to suggest a causal relationship, and other possible contributing factors can be ruled out. The clinical event occurs in a plausible time relationship to study intervention administration and cannot be explained by concurrent disease or other drugs or

chemicals. The response to withdrawal of the study intervention (dechallenge) should be clinically plausible. The event must be pharmacologically or phenomenologically definitive, with use of a satisfactory rechallenge procedure if necessary.

- **Probably Related** There is evidence to suggest a causal relationship, and the influence of other factors is unlikely. The clinical event occurs within a reasonable time after administration of the study intervention, is unlikely to be attributed to concurrent disease or other drugs or chemicals, and follows a clinically reasonable response on withdrawal (dechallenge). Rechallenge information is not required to fulfill this definition.
- **Possibly Related** There is some evidence to suggest a causal relationship (e.g., the event occurred within a reasonable time after administration of the trial medication). However, other factors may have contributed to the event (e.g., the participant's clinical condition, other concomitant events). Although an AE may rate only as "possibly related" soon after discovery, it can be flagged as requiring more information and later be upgraded to "probably related" or "definitely related", as appropriate.
- Unlikely A clinical event whose temporal relationship to study intervention administration makes a causal relationship improbable (e.g., the event did not occur within a reasonable time after administration of the study intervention) and in which other drugs or chemicals or underlying disease provides plausible explanations (e.g., the participant's clinical condition, other concomitant treatments).
- Not Related The AE is completely independent of study intervention administration, and/or evidence exists that the event is definitely related to another etiology. There must be an alternative, definitive etiology documented by the clinician.

7.3.3.2 Expectedness

The Center PI, or designee will be responsible for determining whether an adverse event is expected or unexpected. An adverse event will be considered unexpected if the nature, severity, or frequency of the event is not consistent with the risk information previously described for the study intervention.

7.2.4 Time Period and Frequency for Event Assessment and Follow-up

Adverse events will be recorded from randomization through 6 weeks postpartum. If a serious adverse event occurs after the consent is signed and before randomization, it will also be reported.

Participants will be instructed to contact research staff to report an adverse event that occurs during study participation. In addition, research staff will ask participants at each study visit if they have experienced any side effects or adverse events since the last study visit.

Adverse and Serious Adverse Events will be reported on the Adverse Event Form.

7.2.5 Adverse Event Reporting

7.2.6 Non-serious adverse events must be entered into the study database within 7 days of being notified. Adverse events are reviewed in real-time by PI. Serious Adverse Event Reporting

Any maternal death, neonatal death, or life threatening maternal event must be entered into the adverse events database within 24 hours of being notified, but no later than 72 hours from the onset of the event if it occurs prior to delivery discharge. If a death is reported, a copy of the

participant's de-identified medical record will be uploaded to the adverse events database. Other serious adverse events must be entered into the study database within 7 days of being notified.

Serious adverse events are reviewed in real-time by PI.

7.2.7 Reporting Events to Participants

Participants will not be informed about adverse events, serious adverse events, or study-related results unless the PI decides such information should be reported to participants. As noted in Section 7.2, an Edinburgh depression score of 13 or higher, or a value other than 'never' on the Edinburgh question 10 (harming oneself), will be reported to the participant and the clinical provider.

7.3 Unanticipated Problems

7.3.1 Definition of Unanticipated Problems (UAP)

An investigator may not initiate a change in research activity without single IRB approval unless the change is necessary to eliminate apparent immediate hazards to human subjects, in which case it should be reported to the single IRB as an unanticipated problem (UAP).

The Office of Human Research Protections (OHRP) and the single IRB defines an unanticipated problem as an event that:

- Is unexpected (in terms of nature, severity, or frequency) given the research procedures and the characteristics of the subject population being studied; and
- Is related or possibly related to a subject's participation in the research; and
- Suggests that the research places subjects or others at a greater risk of harm (including physical, psychological, economic, or social harm) than was previously known or recognized.

7.3.2 Unanticipated Problem Reporting

For an event that a PI considers to be an unanticipated problem that is also an adverse event, the AE should be entered into the database within the timeframes established above.

In addition, regardless of whether the UAP is an adverse event or not, a report should be emailed by the PI. The email should contain the following information:

- Protocol identifying information
- A detailed description of the event, incident, experience, or outcome
- An explanation of the basis for determining that the event, incident, experience, or outcome represents a UAP
- A description of any corrective actions that are proposed in response to the UAP

Potential unanticipated problems will be reviewed by PI to determine whether changes to the protocol or consent form should be considered. UAP reports should be submitted through the online IRB system no later than 2 weeks (10 business days) from the notification.

7.3.3 Reporting Unanticipated Problems to Participants

An unanticipated problem will be reported to the specific participant involved. Changes to the protocol or consent form, or the event itself, may also warrant reporting to participants who are currently on study as well as those who have completed the study. In this case, the PI will recommend the course of action (for example, a letter to participants) which will be submitted to the single IRB.

7.4 Participant Discontinuation/Withdrawal from the Study

Participants are free to withdraw from participation in the study at any time upon request.

8 Statistical Considerations

8.1 Statistical Hypotheses

The primary endpoint is the amount of inpatient opioid consumed post-cesarean measured by total morphine milligram equivalents used. The null hypothesis is that there is no difference in amount of inpatient MME in the non-invasive bioelectrical device intervention group compared to sham device group. The alternative hypothesis is that the amount of inpatient MME in the non-invasive bioelectrical device intervention group is less then MME in the sham device group.

Key secondary endpoints include:

- Worst pain score assessed at discharge measured by presence or absence of moderate to severe pain at 1 week post-discharge, defined as a value of 4 or more on the BPI worst pain in the last 24 hours numeric scale (0 to 10).
- Opioid prescription beyond that prescribed at discharge within 6 weeks postpartum
- Opioids prescribed at discharge
- Opioid side effects, wound complications and breastfeeding rates

For the secondary endpoints, the null hypothesis is there is no true difference between the two groups. The alternative hypothesis is there is a difference between the groups. For the key secondary outcomes, the level of significance will be adjusted for multiple comparisons using the false discovery rate method.⁴¹

8.2 Sample Size Determination

Review of inpatient post-operative data, showed that from post-operative day 0 to 2 our patients consume on average MME 42 with SD 15. For 20% reduction in MME to 33.6 and 90% power would need total sample size of 134. Resulting in 67 intervention group and 67 participants in control group.

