1.1 Synopsis

Title:	Non-invasive bioELEctroniC treatment foR pOst-cesareaN (ELECTRON)
Study Description:	This is a randomized trial of 134 individualized post-cesarean delivery who will be randomized to three times use of non-invasive bioelectronic treatment with TrueRelief device or identical appearing sham device for post-cesarean pain management.
Objectives:	Primary : To evaluate whether post-cesarean use of non-invasive bioelectronic treatment reduces inpatient postoperative opioid consumption in morphine milligram equivalents (MME). Secondary : To evaluate whether post-cesarean use of non-invasive bioelectronic treatment 1) improves pain management defined as the presence/absence of moderate to severe pain on post-operative day 2. Moderate to severe pain is defined as a value of 4 or higher on the Brief Pain Inventory worst pain scale (0-10) at discharge, 2) decreases the total amount of opioid tablets prescribed, 3) decreases an opioid refill prescription 4) reduces adverse maternal and infant outcomes.
Endpoints:	Total inpatient opioid consumption in morphine milligram equivalents. Brief Pain Inventory pain severity (worst, least, average, current) in last 24 hours on post-operative day 2, Brief Pain Inventory pain interference during the past week, number of opioid tablets prescribed at discharge, number of opioid prescriptions filled beyond that prescribed at discharge, maternal and infant outcomes.
Study Population:	Individuals with a cesarean delivery who deliver at The Ohio State Wexner Medical Center
Description of Study Intervention:	Non-invasive bioelectronic treatment with TrueRelief device for post-cesarean pain management.
Study Duration:	Recruitment between April 2022 -November 2022. Follow-up, closeout and data analysis by December 2022.
Participant Duration:	6 weeks postpartum

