1.2 Schema

1.3 Schedule of Activities

Measure	Visit 0:	Visit 1:	Visit 2:
	Screening & randomization	Discharge	6-wk postpartum in-person or virtual visit
Informed consent	Х		
Demographics	Х		
Medical history	Х		
Randomization	Х		
Number of inpatient opioids used (MME)		Х	
BPI pain severity		X	
Edinburgh Postnatal Depression Scale			Х
Number of opioids prescribed (MME)		Х	
Opioid prescription refilled (or initially filled if not prescribed at discharge)			Х
Opioid-related side effects		X	

ELECTRON Protocol # 2022H0046

Measure	Visit 0:	Visit 1:	Visit 2:
	Screening & randomization	Discharge	6-wk postpartum in-person or virtual visit
Breastfeeding		Х	Х
Maternal & infant outcomes		Х	Х

2 Introduction

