2.3.3 Assessment of Potential Risks and Benefits

As described above, potential risks are not more than encountered in usual care after cesarean delivery. Treatment with the TrueRelief device may improve pain control and reduce opioid requirements.

3. Study Design

This is a blinded randomized trial of 134 individuals undergoing a cesarean delivery who are randomized after cesarean to three times use of non-invasive bioelectronic treatment with TrueRelief device or identical appearing sham device for post-cesarean pain management.

The primary endpoint is the total inpatient morphine milligram equivalents used during hospital admission. The primary hypothesis is that three times use of non-invasive bioelectronic treatment with TrueRelief device decreases the total inpatient morphine milligram equivalents used during hospital admission compared to use with identical appearing sham device. Consenting women will be assigned in a 1:1 ratio to one of the two arms using a secure internet based randomization system. Individuals will be followed through 6 weeks postpartum.

4. Objectives and Endpoints

OBJECTIVES	ENDPOINTS		
Primary			
To evaluate whether non-invasive bioelectronic treatment reduces inpatient post-cesarean opioid consumption.	Total inpatient postoperative opioid consumption in morphine milligram equivalents (MME).		
Secondary			
To evaluate whether non-invasive bioelectronic treatment post-cesarean decreases opioid refill prescriptions.	Opioid prescription filled (beyond that prescribed at discharge) between discharge and six weeks postpartum.		
	Total number of opioid prescriptions filled by six weeks postpartum (beyond that prescribed at discharge).		
To evaluate whether non-invasive bioelectronic treatment post-cesarean decreases the total amount of opioid tablets prescribed at discharge.	Number of opioid tablets prescribed at discharge.		
To evaluate whether non-invasive bioelectronic treatment post-cesarean reduces pain intensity pain scores	Pain severity scores (worst, least, average, current) in last 24 hours assessed on the Brief Pain Inventory numeric scale from 0 to 10 at discharge		

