8.4.2 Analysis of the Primary Endpoint

The primary outcome is continuous and defined as MME consumed inpatient post-cesarean not normally

ELECTRON Protocol # 2022H0046

distributed and cannot be transformed to approximate normality, the Wilcoxon test and the Hodges-Lehmann estimators of the median will be reported. If normally distributed then paired t-test and mean with standard deviations will be reported.

Analysis of Secondary Endpoint

Secondary outcomes that are binary or categorical will be reported as a proportion with relative risk and 95% confidence intervals as appropriate. For normally distributed continuous outcomes, least squares means general linear regression will be used to estimate means and 95% confidence intervals. For continuous outcomes that are not normally distributed and cannot be transformed to approximate normality, the Wilcoxon test and the Hodges-Lehmann estimators of the median will be reported.

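### Is the power in 8.2, planned on post-operative days 0 to 2, undermined because the primary endpoint runs to discharge?

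*Combined protocol and SAP*

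**What the plan says.** Section 8.2 draws its mean and SD from a review of the site's own inpatient post-operative data: "from post-operative day 0 to 2 our patients consume on average MME 42 with SD 15". It takes a 20% reduction, to 33.6, and 90% power, and arrives at 134 women, 67 per arm.

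The endpoint is described without a day limit. Section 4 gives "Total inpatient postoperative opioid consumption in morphine milligram equivalents (MME"), section 8.1 says "The primary endpoint is the amount of inpatient opioid consumed post-cesarean measured by total morphine milligram equivalents used", and section 8.4.2 says "MME consumed inpatient post-cesarean". Section 3 refers to the hospital admission. Section 7.1.2 collects analgesic "use post cesarean through discharge".

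The nearest link between day 2 and discharge concerns pain. The synopsis (1.1) places one secondary outcome on day 2 ("presence/absence of moderate to severe pain on post-operative day 2") and, in the next sentence, defines it by "a value of 4 or higher on the Brief Pain Inventory worst pain scale (0-10) at discharge". The schedule in 1.3 has a single in-hospital visit after randomization, labelled discharge, and records both inpatient MME and "BPI pain severity" there.

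**The concern.** A power statement applies only to the variable whose mean and SD went into it. If some women stay past day 2, their whole-stay MME includes use that the planning figures left out. That use adds variance. If the device has no effect that late, it adds nothing to the difference between arms.

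The calculation has little room to absorb this: 67 per arm is just enough by the normal approximation, and 8.2 adds no allowance for missing data. There is also a reason to ask whether an effect would last. On the schedule in 6.1.1 the third treatment comes at most 2 + 14 + 14 = 30 hours after surgery. Day 2 ends 48 to 72 hours after surgery by calendar day, so later use would fall at least 48 − 30 = 18 hours after the last treatment. At stake is whether the stated 90% describes the comparison that will be made.

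**Working it through.** **Inputs from 8.2.** Mean 42, SD 15, difference 42 − 33.6 = 8.4, 67 per arm, power 90%. No alpha is given there; two-sided 0.05 is assumed.

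**The plan's figure.** Per arm, n = 2 × [15 × (1.96 + 1.2816) / 8.4]² = 67.01, which matches 67 per arm and 134 in total. The noncentral t distribution gives 89.6% power at 67 per arm and needs 68 per arm for 90%. One-sided 0.05 gives 55 per arm by the normal approximation and does not reproduce 134. The arithmetic is sound for the stated inputs.

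**When the window makes no difference.** Power at a 20% reduction depends only on SD/mean, here 15/42 = 0.357. If nearly all women leave by the end of day 2, or if SD/mean and the 20% reduction carry over to the whole stay, power is unchanged.

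**Illustration with assumed inputs.** A fraction f of women stay past day 2 and use extra MME with mean m (14 or 21) and SD s (7 or 14), independent of earlier use. None of these values is in the documents. The added variance is v = f(s² + m²) − (fm)². Power is by noncentral t with 67 per arm.

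- *No effect after day 2:* difference 8.4, variance 225 + v in both arms.
- *20% cut throughout, day 0 to 2 SD kept at 15 in both arms as in 8.2:* difference 0.2(42 + fm), variance 225 + v (sham) and 225 + 0.64v (device), averaged.

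Worst corner at f = 0.10, m = 21, s = 14: v = 0.10 × (196 + 441) − 2.1² = 59.29. With no later effect, SD = √284.29 = 16.86 and power is 81.7%. With the cut throughout, the difference is 0.2 × 44.1 = 8.82, SD = √(225 + 0.82 × 59.29) = 16.54 and power is 86.5%.

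| f | Power, no later effect | Power, cut throughout |
|---|---|---|
| 0.02 | 87.9 to 89.0% | 88.8 to 89.5% |
| 0.05 | 85.5 to 88.0% | 87.8 to 89.3% |
| 0.10 | 81.7 to 86.6% | 86.5 to 89.2% |

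At 2% the largest loss is 89.6 − 87.9 = 1.7 points.

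**A consistent proportional cut.** If a 20% cut scales every treated woman's use, her day 0 to 2 SD also falls, to 0.8 × 15 = 12. The averaged variance is then (225 + v) × (1 + 0.64)/2. In the worst corner SD = √(284.29 × 0.82) = 15.27 and power is 91.3%. The eight cases at 5% and 10% run from 91.3% to 94.1%. Later use still costs something here, since f = 0 gives 94.4% on the same footing, but power stays above 90%.

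**Is there evidence of stays past day 2?** The subgroup list after 8.4.4 splits time from delivery to discharge at 48 hours. Calendar day 2 ends 48 to 72 hours after surgery, so a woman in the longer group may still leave on day 2. The split shows that stay varies. It does not show that anyone exceeds the planning window.

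**The case for a change.** The strongest case for acting is that the mismatch is plain in the text and cheap to close. The planning figures came from the site's own inpatient data, so the share of women discharged by the end of day 2, or the whole-stay mean and SD, should take one query. The day 2 and discharge wording concerns pain scores, not MME, and nothing applies it to the primary endpoint. With 10% long stayers and no late effect, power could be nearly 8 points below the 89.6% that 67 per arm gives.

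Part of this stands: no sentence in the plan equates the two windows, and one would help a reader. The rest does not lead to a change. The size of the loss comes entirely from assumed stays and assumed late use. Late use falling at least 18 hours after treatment rests on 6.1.1 alone; 6.1.2 and 2.3.1 describe the timing in terms that do not fix a 30-hour limit, and those sections must be reconciled as a separate matter. Ending the primary endpoint at day 2 would demote total inpatient consumption, which is the stated objective. Women who leave early would still contribute a shorter period. That exchanges one imperfection for another.

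**Conclusion.** No change to the plan follows. Section 8.2 leaves unsaid that its day 0 to 2 figures stand for the inpatient stay. That is the natural reading, given a single in-hospital assessment visit at discharge and pain scores timed both on day 2 and at discharge. The 134 reproduces at an assumed two-sided 0.05, with 89.6% power by t-test, and no stated figure is shown to be wrong. If long stayers are rare (2%), the loss is at most 1.7 points. At 5 to 10% the illustration gives 81.7 to 89.3% with the common SD of 8.2 and 91.3 to 94.1% with a consistent proportional cut. The documents do not say which case applies. The planning window affects only how well power was foreseen: the comparison of randomized arms on whole-stay MME is valid either way, and its confidence interval will show the precision achieved. The conclusion assumes that most women leave by the end of day 2, which the documents suggest but do not state.
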